## **11. ANALYSIS FOR THE ACQUISITION STUDY**

This study is designed to evaluate the use of the new curved paddle including image quality, patient comfort and tissue coverage. Data in the form of questionnaires will be collected from the subject, technologist and radiologist. A synthetic 2D image may be created for all 3D images and will be included in the image review. The Hologic synthetic 2D image is called C-View and is FDA approved. The investigational C-View images for the curved paddle will be used for image comparison only and not for clinical evaluation.

Each patient will have their images reviewed by an appointed study radiologist who will be asked to rate and compare the standard of care images to the investigational images using a 5 point Likert scale for:

- Overall Image quality
- Lesion visibility
- Tissue separation of structures
- Tissue coverage (especially at the Chest wall, axilla and Infra-mammary fold)
- Patient Motion

The radiologist will also assess breast density separately on the standard of care and on the investigational images.

The image review will consist of a side-by-side comparison with the standard-of-care image displayed on one display monitor and the matching investigational image on another display monitor.

No formal power calculation has been performed, because of the descriptive nature of the trial. A total of 650 patients will be enrolled in the study.

All variables will be tabulated using descriptive statistics. Continuous variables will be presented as means and standard deviations with 95% confidence intervals, as well as medians and ranges. For categorical variables, relative frequencies and 95% confidence intervals will be provided.

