## 6. INVESTIGATIONAL DEVICE DESCRIPTION

Image processing software and an investigational curved paddle will be employed on a commercially approved Hologic Selenia Dimensions mammography system. The investigational paddle is made from a plastic material shaped with a curve to conform better to breast anatomy. The breast tomosynthesis system is a digital mammography system that is capable of producing standard two-dimensional (2D) images and three-dimensional (3D) tomosynthesis images. The Hologic Dimensions system is a commercial product approved by the FDA. The image processing software will only be applied to images acquired with the investigational paddle which is identified via an RFID tag on the paddle when it is attached to the Dimensions.

**Figure 3:** Investigational paddles of different sizes showing the curved shape

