### **7.2 Secondary Endpoints**

1. Tissue volume imaged with curved paddle is greater than that for standard paddle
2. Image quality when using the curved paddle is non-inferior to the image quality of the standard paddle

This study will investigate and measure the potential reduction in pain to the breast with the curved paddle when compressing breast tissue to tautness as compared to the standard of care paddle compressing breast tissue to tautness. The potential improvement in the comfort of a mammographic exam for patients while looking at ease in positioning for technologists, without a loss in image quality, would offer a less painful, high quality procedure, which may potentially increase mammography compliance rates.

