650 women who are at least 40 years of age will be enrolled. Data will be recorded for compression related parameters such as compression force, thickness, and comfort for both conventional and investigational paddle designs. A standardized 10 point pain scale will be used to record comfort. The investigational paddle that will be tested has been constructed with the natural shape of the breast in mind, rather than current paddles which are straight and flat to try to flatten the breast. In order to obtain the necessary information related to the images, radiologists will be asked to evaluate overall image quality between the standard of care paddle and the investigational paddle.

Each subject will be instructed on the use of the pain scale. The investigational imaging using the Curved Paddle (C-paddle) will be conducted on one breast in either the screening or the diagnostic study population for this study.

At the time of enrollment all screening subjects must be at least 40 years of age and all diagnostic patients must be at least 25 years of age, and be scheduled to have a mammogram as part of their routine clinical care. All subjects will be required to sign an informed consent form prior to enrollment and undergoing imaging with the investigational paddle in the study. All exams will be conducted on the same day. At the

conclusion of the procedure each subject will be asked a few questions related to her overall experience during the visit and her preference for which paddle she preferred.

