## **10. DETAILED STUDY PROCEDURE**

A study flow chart is shown below. The study will include 650 subjects. After determining eligibility and informed consent is obtained, the subjects presenting for screening will undergo (2D plus 3D) with the current paddle and 2 views of one breast with the curved paddle (CC and MLO in 2D plus 3D).

[figure not shown]
If the patient is undergoing diagnostic imaging she will have her prescribed diagnostic views followed by a combination (2D plus 3D) CC or MLO with both the standard paddle and the investigational curved paddle compressed to tautness on the breast of interest.

In both the screening and the diagnostic populations, the paddle order will alternate so that for the first subject the order would be standard of care, followed by the investigational paddle. The next subject would have the investigational first followed by the standard of care. The order is changed to prevent distortion in the recorded pain scores since women may find the first compression more or less painful than subsequent compressions.

Both sets of compression on the curved paddle and the standard of care paddle will be to tautness. The force will not be matched exactly since the curved compression paddle may allow imaging of more breast

tissue and forcing the compression level to match the standard of care may result in unnecessary pain to achieve tautness. The technologist will strive to achieve a similar compression without causing excess pain.

[figure not shown]
**Figure 4:** Flowchart showing the enrollment and imaging process

The technical factors such as kilovoltage, tube current and filtration will be determined using AEC (automatic exposure control) in the same manner as conventional 3D exams.

At the completion of each compression for each view and each paddle (the standard procedure and the investigational procedure(s)) each patient will be asked to rate her pain on a 0-10 pain scale. The result will be pain scores for the breast being compressed with both paddles. Additionally, each patient will be asked to point out any specific areas of discomfort on a breast diagram that is experienced during the course of the compression procedures.

**Figure 5:** Pain score used for comfort evaluation

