The investigational images will not be used to recommend biopsy and will not be used to cancel work-up or biopsy of any index lesion of concern that was recommended based on the standard of care (SOC) mammograms. However, the investigational images may characterize the index lesion of concern as more suspicious than standard diagnostic imaging and further standard work-up (including targeted extra views, sonography or MRI) may be recommended. The subject and the subject's doctor will be informed of any new finding(s). The subject is not required to undergo further testing.

The investigational images may also allow detection of a new suspicious finding and further standard work-up (including targeted extra views, sonography or MRI) may be recommended. The subject and the subject's doctor will be informed of any new finding(s). The subject is not required to undergo further testing.

If a patient is recalled based on her standard of care imaging, her follow-up procedures will be outside of this study and be conducted as per institutional policy for patient care.

The study technologist conducting the study imaging will then complete a series of questions regarding their experience with the procedures for both paddles using a 5 point Likert scale to compare the investigational procedures against the Standard of Care procedures for areas including but not limited to:

- Overall Ease in positioning for each view on each paddle
- Ability to maintain positioning
- Ability to get high into the Axilla
- Ability to get further back on the chest wall
- Ability to pull in more tissue
- Ability to decrease skin folds
- Ability to decrease neck pulling
- Ability to decrease breast sagging
- Ability to hold the breast in the optimal MLO position

After the images have been acquired a study radiologist will conduct a side by side image comparison of the standard of care images to the investigational images using a 5-point Likert scale to assess the images for:

- Overall Image quality
- Lesion Visibility
- Tissue separation of structures
- Patient Motion

The radiologist will also assess breast density separately on the standard of care and on the investigational images.

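### The side-by-side read behind the non-inferior image-quality endpoint has no described masking of paddle type and no described variation of monitor side

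*Combined protocol and SAP*

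**What the plan says.** The second secondary endpoint in Section 7.2, repeated in the Executive Overview, is: "Image quality when using the curved paddle is non-inferior to the image quality of the standard paddle". Section 4 gives the same condition as part of the primary aim: better comfort with no loss of image quality.

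Three places describe the assessment.

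- Section 9 says that "radiologists will be asked to evaluate overall image quality between the standard of care paddle and the investigational paddle", without giving a method.
- Section 10 says that "a study radiologist will conduct a side by side image comparison of the standard of care images to the investigational images", on a 5-point Likert scale.
- Section 11 has one appointed study radiologist per patient "rate and compare the standard of care images to the investigational images using a 5 point Likert scale for" items that include overall image quality and tissue coverage. The display is a "side-by-side comparison with the standard-of-care image displayed on one display monitor and the matching investigational image on another display monitor".

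For the analysis, Section 11 says: "For categorical variables, relative frequencies and 95% confidence intervals will be provided". It also calls the trial descriptive and reports no formal power calculation. No non-inferiority margin is given.

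**The concern.** The rating is a subjective comparison of two images. A reader who knows which image is investigational may lean towards or against it. A reader who favours one monitor would also lean, and if the curved-paddle image always sits on the same side, that preference is indistinguishable from a paddle effect.

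Such a lean is bias, not noise. A lean shared by all readers does not shrink with more patients or more readers. Leans that differ between readers average out only over the number of readers. That number is not stated; the Executive Overview gives 4-5 sites. The planned 95% confidence intervals reflect neither kind.

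The plan already varies paddle order to protect the pain scores. It describes no counterpart for the read that carries the image-quality endpoint. The same read scores tissue coverage, which bears on the other secondary endpoint as the Executive Overview words it.

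**Working it through.** **Text check.** The nearest safeguards in the documents do other jobs.

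- The paddle order in Sections 9 and 10 governs compression and pain scores, not image display.
- Removal of identifiers in Sections 18.1 and 18.3 concerns the subject's identity, not the paddle.
- The technologist's image review in Section 13 is system quality control.
- The separate read of each image set in Sections 10 and 11 is for breast density, not image quality.

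No supplied passage states masking, label removal, or a rule for the monitor side.

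**Inputs.** The plan has no figure to reproduce for this endpoint. From the plan: n = 650 ratings (the planned maximum, taking one rating per patient). Assumed: no true difference; share rated *same*, t = 40% to 80%; share of those tipped to one image by a shared lean, q = 0% to 10%; independent ratings; the five levels collapsed to better, same and worse.

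**Formulas, constant lean towards the curved image.**

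- better = (1 − t)/2 + qt; same = t(1 − q); worse = (1 − t)/2
- D = better − worse = qt, which is all bias
- SE = √[(better + worse − D²)/n]; half-width = 1.96 × SE
- coverage of the true zero = Φ(1.96 − D/SE) − Φ(−1.96 − D/SE)

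**Mid case, t = 0.60, q = 0.05.** better = 0.20 + 0.03 = 0.23; worse = 0.20; D = 0.03. SE = √[(0.43 − 0.0009)/650] = 0.0257. Half-width = 0.050. D/SE = 1.17, so coverage is 78.5%.

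| Same | Tipped | Shift (points) | Half-width (points) | Coverage |
|---|---|---|---|---|
| 40% | 0% | 0 | 6.0 | 95% |
| 40% | 5% | 2.0 | 6.1 | 90.1% |
| 40% | 10% | 4.0 | 6.1 | 75.2% |
| 60% | 0% | 0 | 4.9 | 95% |
| 60% | 5% | 3.0 | 5.0 | 78.5% |
| 60% | 10% | 6.0 | 5.2 | 38.0% |
| 80% | 0% | 0 | 3.4 | 95% |
| 80% | 5% | 4.0 | 3.8 | 44.9% |
| 80% | 10% | 8.0 | 4.0 | 2.6% |

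At 325 ratings the shifts are unchanged and the half-widths run from 4.9 to 8.7.

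**Check without collapsing the scale.** Take the mean 5-point score with an assumed SD of 1.0. The half-width is 1.96 × 1.0/√650 = 0.077. A constant shift of 0.1 point with no true difference makes the interval exclude zero with probability 0.722. Over assumed SDs of 0.5 to 1.25 that probability runs from 0.999 to 0.532.

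**Leans that differ between readers.** Assume one reader per site and independent leans with SD 3 points. The average lean then has SD 3/√4 = 1.5 points with 4 readers and 3/√5 = 1.3 with 5, however many patients each reads.

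**What the remedies remove.** Let m be the part of the lean that is monitor preference and r the share of curved-paddle images still recognised after masking. With random side and masking, the residual is shift × (1 − m) × r. For a 6-point shift:

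- m = 1: 0
- m = 0.5, r = 1: 6 × 0.5 = 3
- m = 0.5, r = 0.5: 6 × 0.5 × 0.5 = 1.5
- m = 0, r = 0.5: 3
- m = 0, r = 1: 6, so nothing is gained

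**The same-or-better percentage, mid case.** With no lean it is 60% + 20% = 80%. A constant lean towards curved gives 57% + 23% = 80%, a change of 0. A constant lean towards standard gives 57% + 20% = 77%, a fall of 3.0 points. If the lean is all monitor preference, random side averages the two and gives a fall of 1.5.

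**The case against.** The strongest reply is that this is a silence in the text and not a stated flaw. The documents do not say that the reader is told the paddle, or that the side is constant. This stands, and the monitor part of the point is conditional for that reason.

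Second, no consequence is shown. The inputs are assumed, the range starts at zero, the mid-case shift lies inside the half-width, and the endpoint is secondary in a trial the plan calls descriptive. This limits the weight of the point. It does not remove it, because descriptive frequencies can be biased too and the endpoint is still worded as non-inferior.

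Third, masking may achieve little. Section 6 says: "The image processing software will only be applied to images acquired with the investigational paddle". Section 10 adds that "the curved compression paddle may allow imaging of more breast" tissue. Either could reveal the paddle. This stands as a limit on the remedy.

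Fourth, better-minus-worse is not a summary named in the plan, and on a same-or-better percentage random side can help or hurt. This also stands, and it is a reason to tabulate the full scale.

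A reader might go further and infer that the read is known to be unmasked with a fixed side, that it favours the curved paddle, or that a non-inferiority conclusion would be wrong. The documents support none of these: they are silent on masking and side, give no evidence on direction, and state no margin against which to judge a shift. Nor can one infer that 650 patients would wash out everything except a lean common to all readers, since reader-specific leans depend on how many readers there are.

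**Conclusion.** The point holds as a cheap improvement to a subjective read, not as a demonstrated error. The only comparison described for this endpoint is open to bias from knowledge of the paddle and, if the side is constant, from monitor preference.

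On the assumed inputs the shift in better-minus-worse runs from 0 to 8 points against half-widths of 3.4 to 6.1 at 650 ratings. These are illustrations. They rest on no true difference, an invented range for ties and lean, a lean shared across readers, and independent ratings with no clustering by reader. The low coverage figures belong to the extreme corner of that range and are not predictions. If there is no lean, nothing is lost and the change gains nothing.

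**What to change.** Amend Section 11, with matching text in Section 10, for the comparison read only:

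1. Remove paddle and processing labels from the displayed images where feasible.
2. Assign the curved-paddle image to the left or right monitor at random per case.
3. Have the reader score left versus right on the 5-point scale and record the score before labels are shown.
4. Decode at analysis. Tabulate the full 5-point distribution, then curved better, same and worse, with the better-minus-worse difference and its 95% confidence interval, overall and by reader.

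Keep the same readers and the same number of reads. The separate density read and the reporting of new findings stay as they are, since labels are shown once the score is recorded.

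**Cost.** A display step for up to 650 cases at 4-5 sites, covering 2D, 3D and possibly synthetic 2D images; a random side list; a way to fix the score before labels appear, which the paper files and spreadsheet in Sections 18.2 and 18.3 do not obviously provide; and a few lines of decoding. No extra readers, reads or radiation.

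**Limits to state in the plan.** Masking may be only partial. Random side removes monitor preference but not the bias of a reader who recognises the paddle. It balances better-minus-worse but not a same-or-better percentage. The non-inferiority margin remains a separate gap.

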## **12. STUDY DURATION**

Subjects will be accrued over a 24-month period. The amount of time each subject will actively participate, inclusive of the consenting process, will be approximately 30-60 minutes. Once imaging is complete, the subject will be cleared to leave the facility per standard Imaging protocol. Subjects will be considered as enrolled subjects from the time they complete and sign the informed consent until the time they complete the imaging procedures or ask to be withdrawn from the study.

## **13. QUALITY CONTROL**

The Hologic Selenia Dimensions Digital Mammography Systems with the investigational paddle will be checked by a qualified medical physicist prior to any testing or imaging of subjects to assure the system is operating correctly. A Study Technologist will review the tomosynthesis images, obtain phantom images and check system operation on a periodic basis to ensure system performance. The quality control procedures described in the systems' operator manuals will be used throughout the trial. If there is any noticeable degradation in system performance, a Hologic engineer will be called immediately to recalibrate or repair the system.

Routine QC procedures will be run on the system per the manufacturer instructions.

## **14. POTENTIAL RISKS AND ANTICIPATED BENEFIT TO THE SUBJECT**

An immediate benefit to the subject being enrolled in the study is not anticipated, although participation in this study may lead to the use of a more comfortable, more specific tool for evaluating breast disease for the benefit of future patients. It is possible that the additional imaging tests could identify a significant additional lesion not identified by the standard imaging paradigm.

### **14.1. Radiation risk**

Although the 2D and 3D mammograms are FDA approved imaging modalities, a risk of the proposed study is the additional radiation exposure for enrolled subjects in having an additional two 2D/3D combination image pairs of one breast. The estimated mean glandular radiation dose for each 2D plus 3D image will be 2.9 mGy for an average breast size (4.2 cm compressed breast thickness). For two investigational images, the imaged breast would receive on average about 5.8 mGy (=2.9 mGy x 2) of radiation dose. The *average* additional breast dose would be half this, 2.9 mGy, since the other breast is not imaged with the investigational paddle.

To calculate risk from radiation, the most common approach is to relate the radiation dose to a whole body exposure. The International Commission on Radiation Protection states that exposure to the breasts results in a risk approximately equivalent to 12% of that from whole body exposure [1].

To calculate the equivalent whole body radiation dose of the investigational exam, the average breast dose would be 2.9 mGy. Therefore the expected whole body equivalent dose based on two investigational combo images would be;  $2.9 \text{ mGy} \times 12\% = 0.35 \text{ mSv}$ .

The additional radiation from participation in this study is very low and may be compared to natural background radiation dose that is approximately 1.5 mSv per year in the US. This value includes background radiation from cosmic radiation and radon. The additional radiation dose from this study is therefore equivalent to about 3 months of the average background radiation dose or less and is therefore not considered to be a significant risk to the subject.

Therefore, it is felt that participation in the clinical study will not present a significantly increased risk to participating subjects.

#### **14.2. Other potential risks**

Other potential risks of the research mammograms are those similar to having standard mammography and include the possibility of bruising, infection and skin irritation, and abrasion wounds from compression of the breasts, but this is extremely unlikely. Millions of mammograms are performed each year with a very low occurrence of such incidences.

### **15. NEW FINDINGS**

The investigational images may reveal a new suspicious finding and additional imaging (mammograms, sonography or MRI) may be recommended. The participant subject and her doctor will be informed of any new suspicious finding on the study mammograms, but the subject is under no obligation to undergo further testing. The new finding may prove to be an otherwise occult cancer, thus providing for an earlier detection. Early detection of breast cancer is associated with reduced morbidity and an improved outcome. Conversely, the new suspicious finding detected on the study mammograms may prove to be normal or benign. In this case, the participant subject may incur unnecessary additional time and anxiety.

The likelihood of new suspicious findings is low because the standard imaging already includes 3D imaging.

### **16. COMPENSATION**

Subjects will be compensated for participation in this study. If site allows, subjects will be

compensated up to the amount agreed upon in the Clinical Trial Agreement and Informed Consent Form.

## **17. ALTERNATIVE PROCEDURES**

No diagnosis or treatment is offered in this study. The alternative is to not participate in the research study. Not participating will not affect the subject's relationship with her physician, nor the subject's right to health care or other services to which she is otherwise entitled.

Participation in this study will in no way delay the standard care for the patient.

